5.8 Days 1-7 (0-168 hours)

- The first dose of glyburide must be administered within 8 hours of injury and stopped after 72 hours. Hard stop rules for glyburide administration are listed below.
- As per recommended standard-of-care guidelines [3], subjects will be admitted to the intensive care unit following initial diagnostic testing where continuous respiratory, cardiac, and hemodynamic monitoring will be undertaken [32]. Maintenance of normal blood oxygenation and a mean arterial blood pressure of 85-90 mmHg will be emphasized in this monitored setting continuously over the first full 7 days following injury.

- The following assessments will be performed through day 7 following injury (during and after study drug regimen):
 - Safety labs: 24 hours (± 12 hours), 48 hours (± 12 hours) 72 hours (± 12 hours) and 96 hours (± 12 hours).
 - Hematology: complete blood count
 - Chemistry: electrolytes (sodium, potassium, chloride, bicarbonate), BUN, creatinine
 - Liver Function Tests: AST, ALT, bilirubin (total and direct), and alkaline phosphatase
 - Blood glucose (BG) monitoring will be hourly (± 30 minutes) for Hours 1-24, every 2 hours (± 30 minutes) for Hours 25-48 and every 4 hours (± 60 minutes) for Hours 49-88. If BG < 70 mg/dL, BG monitoring is required every 15 (± 10 minutes) minutes until BG ≥ 80 for 3 consecutive readings without exogenous bolus glucose supplementation, then hourly (± 30 minutes) for the next 12 hours and every 2 hours (± 30 minutes) thereafter.
 - Continuous bedside cardiac telemetry monitoring from Hour 0 through Hour 72
 - ECG (12-lead) at 4-6 hours, 24 \pm 6 hours, 48 \pm 6 hours and 60-72 hours (from the start of study drug regimen). The ECGs will be read within 12 hours, recorded as clinically significant or non-clinically significant, and signed off on by study team member.
 - Blood sampling for PK prior to dosing, at 4-6 hr (prior to the second study drug administration), 24 \pm 6 hours, 48 \pm 6 hours and 60-72 hours.
 - PK Samples to be drawn as close as possible to ECGs
 - Start time of drug and time of subsequent dosing. Record reason for any missed doses.
 - Concomitant medications and procedures/therapies
 - Review safety and AEs
 - ASIA Impairment Scale scoring at 24 \pm 12 hours, 48 \pm 12 hours, 72 \pm 12 hours, and 96 \pm 12 hours. In the event of spinal fracture reduction (closed or open with additional stabilization), an additional ASIA evaluation must be recorded as close to the start of the procedure as possible, preferably within

2 hours. Every attempt should be made to collect the ASIA grading free of the effects of sedating drugs.

- Blood sampling for additional laboratory tests to identify biomarkers prior to dosing and at 1, 3 and 7 days
- Cervical MRI scans performed on admission and on Day 2 will be uploaded to REDCap.

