In a phase 1 study of intravenous glyburide (Cirara™), the drug was administered as a bolus dose followed by a 3-day continuous infusion maintenance dose. Five groups of patients were dosed, totaling 26 patients on drug (4 dosing groups, with doses ranging from 0.4 to 10 mg/day) and 8 on placebo. There were no SAEs during the study. Two subjects (one in the 6 mg/day treatment group and one in the 10 mg/day treatment group) were discontinued from the study due to persistent hypoglycemia. The subject in the 6 mg/day treatment group who was discontinued from the study also experienced transient increases in ALT and AST levels beginning 3 days after study drug discontinuation, which returned to normal by Day 22. There were no other clinically significant drug-related AEs [1]. Based on this work, Phase 2a pilot and exploratory randomized trials were undertaken by Remedy Pharmaceuticals (GAMES-RP) wherein a total of 93 stroke patients were dosed at 3 mg/day for 3 days. There were no new safety concerns raised in these patients [36].

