5.5 Study Drug Description, Dose, and Administration

Enrolled patients will receive 12 doses of glyburide starting within 8 hours of SCI. The dosing regimen involves an initial dose of 1.25 mg followed by eleven consecutive doses of 0.625 mg every 6 hours. The total daily dose of glyburide on Day 1, Day 2 and Day 3 will be 3.125 mg, 2.5 mg, and 2.5 mg respectively (see Table 2).

Table 2: Study Dosing

	Day 1	Day 2	Day 3
Total Dose	3.125 mg	2.5 mg	2.5 mg
	First dose of 1.25 mg then 0.625 mg every 6 hours	0.625 mg every 6 hours	0.625 mg every 6 hours

This injury-to-drug timeframe will apply to patients managed non-operatively as well as to patients undergoing surgery (likely a majority of patients in the trial). Drug administration should not be stopped as the standard of care diagnostic studies and treatment is provided, including if the patient is transferred to the OR for decompression and stabilization. Hard stop rules for glyburide administration are listed below.

In the event a dose of glyburide is missed (beyond 2.5 hours from the expected administration time), the next dose should be administered at 1.25 mg followed by the usual 0.625 mg dose for subsequent administrations. If the missed dose is acknowledged within 2.5 hours of the expected administration time the dose should be given and the deviation noted.

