5.9 Up to day of discharge (but no later than Day 14)

In addition to continuous review of safety and AEs during the second week of hospitalization (up until discharge, as applicable), the following evaluations and assessments will be performed prior to Day 14 or Discharge, whichever is earlier:

- ASIA Impairment Scale scoring. Every attempt will be made to collect scores free of the effects of sedating and/or paralytic drugs.
- Concomitant medications
- Safety labs:
 - Hematology: complete blood count
 - Chemistry: electrolytes (sodium, potassium, chloride, bicarbonate), BUN, creatinine, glucose
- Liver Function Tests: AST, ALT, bilirubin (direct and total), and alkaline phosphatase
- Concomitant procedures and therapies
- Contact information for the subject (home and cellular telephone numbers, email addresses, home addresses, rehabilitation or nursing home information including fax and phone numbers); LAR (home and cellular telephone numbers, email addresses, home addresses); family members (home and cellular telephone numbers, email addresses, home addresses); and personal physician (phone and fax numbers)

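### Fixed-time liver panels end before the one delayed ALT/AST rise the protocol cites would begin; the single later panel has no earliest time and may miss or fail to date it

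*Combined protocol and SAP*

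**What the plan says.** **Dosing (section 5.5).** "Enrolled patients will receive 12 doses of glyburide starting within 8 hours of SCI", given as "an initial dose of 1.25 mg followed by eleven consecutive doses of 0.625 mg every 6 hours". Section 5.8 adds: "The first dose of glyburide must be administered within 8 hours of injury and stopped after 72 hours".

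**Fixed liver tests (section 5.8).** AST, ALT, bilirubin and alkaline phosphatase belong to the safety bloods, which are timed as "Safety labs: 24 hours (± 12 hours), 48 hours (± 12 hours) 72 hours (± 12 hours) and 96 hours (± 12 hours"). Whether these hours run from injury or from first dose is not stated; the ECGs in the same list are timed from the start of study drug.

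**Later liver test (section 5.9).** One further panel is required: "the following evaluations and assessments will be performed prior to Day 14 or Discharge, whichever is earlier". No earliest time is given.

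**Calendar (section 5.11).** The Labs row is marked at screening, on Days 1 to 4 and at Day 14 or discharge. Day 7 is blank, as is every visit from Day 28 on. Blood is nevertheless drawn on Day 7 for another purpose (section 5.8): "Blood sampling for additional laboratory tests to identify biomarkers prior to dosing and at 1, 3 and 7 days".

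**The prior event (section 2.2).** In the phase 1 study of intravenous glyburide, one subject in the 6 mg/day group, stopped for persistent hypoglycemia, had "transient increases in ALT and AST levels beginning 3 days after study drug discontinuation, which returned to normal by Day 22". In all, 26 subjects received drug, at 0.4 to 10 mg/day.

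**The concern.** Safety is a primary objective, and section 3.1 promises continuous monitoring of laboratory results during the hospital stay. The protocol describes one delayed liver-enzyme event and gives its latency, but the laboratory schedule is not tied to that latency: the regular panels stop on Day 4.

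A rise that shows only in the laboratory is found only if blood is tested while it is present. Section 6 also asks for start and end dates for each adverse event and for a judgement of relatedness to glyburide. A single late value supports neither well. The data are meant to inform a phase II/III design, so a report of no hepatic finding should come with evidence that patients were tested when such a finding could appear.

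**Working it through.** **Step 1. Reproduce the dosing timeline.** Dose k is given at 6 × (k − 1) h, so dose 12 falls at 6 × 11 = 66 h. Check against section 5.5, which states "The total daily dose of glyburide on Day 1, Day 2 and Day 3 will be 3.125 mg, 2.5 mg, and 2.5 mg respectively":
- Day 1: 1.25 + 3 × 0.625 = 3.125 mg.
- Days 2 and 3: 4 × 0.625 = 2.5 mg each.

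The totals agree, so 66 h is the last-dose time the plan implies.

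**Step 2. Last fixed panel.** 96 ± 12 h gives a window of 84-108 h.
- First-dose clock: 84 − 66 = 18 h to 108 − 66 = 42 h after the last dose.
- Injury clock, with the first dose 0-8 h after injury: last dose at 66-74 h, so 84 − 74 = 10 h to 108 − 66 = 42 h after it.

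**Step 3. Expected onset.** Assume the cited 3 days means 72 h and applies after a full course. Count it either from the last dose or from the 72 h stop.

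| Clock | From last dose | From 72 h stop |
|---|---|---|
| First dose | 66 + 72 = 138 h | 72 + 72 = 144 h |
| Injury, first dose at 8 h | 74 + 72 = 146 h | 80 + 72 = 152 h |

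The range is 138-152 h.

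**Step 4. Gap.** The latest permitted fixed panel precedes onset by 138 − 108 = 30 h to 152 − 108 = 44 h. From the nominal 96 h draw the gap is 42-56 h. No fixed panel reaches onset after a full course on either clock.

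**Step 5. The Day 14/discharge panel.** Drawn at Day 14 (336 h), it falls 336 − 152 = 184 h to 336 − 138 = 198 h after onset, about 8 days. Drawn at a discharge before about 138-152 h, it precedes onset and nothing follows it.

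**Step 6. A panel on Day 7.** At 168 h it falls 168 − 152 = 16 h to 168 − 138 = 30 h after onset. At 144 h it would fall anywhere from 6 h after onset to 8 h before it. The draw therefore needs a window near 168 h.

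**Step 7. Early stopping.** On the first-dose clock, a last dose at or before 96 − 72 = 24 h (108 − 72 = 36 h at the window edge) would let the final fixed panel reach a 3-day onset. The gap is specific to full or nearly full courses.

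**Step 8. How much 10 patients can show.** At an assumed rate of 1/26 = 3.8%, the chance of at least one case in 10 is 1 − (25/26)^10 = 32%. The exact 95% interval for 1/26 is 0.1% to 19.6%, which carries that chance from about 1% to about 89%. Zero cases in 10 leaves a one-sided 95% upper limit of 1 − 0.05^(1/10) = 25.9%, even with perfect ascertainment.

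**The case against.** The strongest reply is that section 5.9 already covers the period. It follows the section on Days 1-7, opens with the second week in hospital, and requires the full liver panel. Section 5.8 plans intensive care with blood-pressure support through the first 7 days after injury, so most patients managed as described would have that panel after 152 h. The phase 1 rise was reported normal only by Day 22, so a Day 14 panel might still show it. This largely stands. A reader might infer that no liver test follows 96 h, or that the schedule is bound to miss the event; the documents support neither. What remains is that detection depends on one value, and the duration of the phase 1 rise is not given.

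Second, the evidence is thin: one subject, at 6 mg/day intravenously, against 2.5-3.125 mg/day orally here. Section 2.2 also reports 93 stroke patients at 3 mg/day with no new safety concerns. This stands. Calling the event a known hepatic signal, or a silent one, goes too far, since the documents do not say whether that subject had symptoms. The 32% in Step 8 should not be quoted without its range.

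Third, clinically evident hepatic events would be recorded as adverse events through Day 28, and section 4.3 lists blood work as standard of care. The first part stands, so only a laboratory-only rise is at issue. Section 4.3 does not say which tests are run or when, so it cannot be relied on for liver enzymes.

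Fourth, a Day 7 panel does not reliably reach patients discharged before Day 7. This also stands.

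**Conclusion.** The point holds as a limited gap in ascertainment. After a full course, no fixed-time liver panel reaches the onset implied by the protocol's own cited latency; the shortfall is 30-44 h from the latest permitted draw, whichever clock is used. The later panel should follow onset in most patients who complete the 7-day monitored period, but it cannot date onset or peak and may miss a short rise. Discharge before about Day 6-7 leaves no liver test after onset.

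This assumes that the latency of a single intravenous case carries over to an oral course at a lower daily dose, and that 3 days means 72 h. The schedule is also not the only limit: with 10 patients, zero cases could not exclude a rate of up to about 26%. The change is worth making because it is cheap and serves a primary objective, not because the documents show that a hepatic effect will be missed.

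**What to change.** 1. In section 5.8 and the calendar, add AST, ALT, bilirubin and alkaline phosphatase to the existing Day 7 biomarker draw, with a window placed near 168 h so that it falls after 152 h.
2. In section 5.9, state that the Day 14/discharge panel is a separate, later sample for patients still in hospital.
3. State whether the safety-laboratory hours run from injury or from first dose.
4. In section 7.0, report peak post-dose ALT and AST, and the number of patients with no liver test after about 152 h, so that an absence of findings can be read against what was measured.

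These changes concern ascertainment only and set no treatment rule. The cost is at most 10 extra routine panels on blood already being drawn, a calendar entry, and possibly a few incidental abnormal values to report. Patients discharged before Day 7 may still be uncovered; the count in item 4 makes that visible.

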2.2 Glyburide and Signaling Background

Glyburide (also known as Glibenclamide; 5-chloro-N-(4-[N-(cyclohexylcarbamoyl)sulfamoyl]phenethyl)-2-methoxybenzamide) is an anti-diabetic medication in a class of medications known as sulfonylureas. In treating NIDDM, the drug works by inhibiting ATP-sensitive potassium channels in pancreatic beta cells by antagonism of SUR1. This inhibition causes cell membrane depolarization, which causes voltage-dependent calcium channels to open, which in turn causes an increase in intracellular calcium in the beta cell, stimulating insulin release.

The Sur1-Trpm4 channel is selectively expressed in the central nervous system (including the spinal cord) under conditions of ischemia, hypoxia, and trauma [6, 8-10], leading to vasogenic and cytotoxic edema followed by oncotic cell death [11]. With respect to micro vascular endothelial cells, this process leads to the formation of space- occupying edema and secondary hemorrhage. Spinal cord edema and micro hemorrhage formation through this mechanism is a critical secondary injury process that progressively exacerbates mechanical compression, ischemia, and neuronal/glial cell death following trauma [12].

Numerous pharmacokinetic studies of oral glyburide have assessed single-dose administrations in normal subjects and have demonstrated significant absorption within one hour, peak drug levels at about four hours, and low but detectable levels at twenty-four hours. Mean serum levels of glyburide, as reflected by areas under the serum concentration-time curve, increase in proportion to corresponding increases in dose. Multiple-dose studies with glyburide (a widely available oral glyburide formulation) in diabetic patients demonstrate drug level concentration-time curves similar to single-dose studies, indicating no build-up of drug in tissue depots. The decrease of glyburide in the serum of normal healthy individuals is biphasic, the terminal half-life being about 10 hours [34].

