The dosing regimen can only be reduced twice; if (i) or (ii) above occurs a third time, glyburide must be discontinued. Glyburide dosage must only be stopped based on verified laboratory test values or, if not available, a repeat point-of-care that are taken 15 minutes or more following the last administration of insulin. When glyburide is stopped as a result of low BG, D50W should be administered by bolus in order to maintain BG > 80 mg/dL. Multiple D50W boluses may be administered, the timing and volume of which are at the discretion of the clinician. BG monitoring is required every 15 (\pm 10) minutes until BG \geq 80 for 3 consecutive readings without bolus glucose supplementation, then hourly (\pm 30 minutes) for the next 6 hours.

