5.11 Study Calendar

Test and Observations	Screening / Enrollment (up to 6 hours prior to treatment)	Day 1	Day 2	Day 3	Day 4	Day 7	Day 14 or D/C	Day 28 (+/- 7 days)	Day 42 (+/- 7 days)	Day 84 (+/- 14 days)	Day 182 (+/- 14 days)	Day 365 (+/- 30 days)
History & Physical	X											

Vital Signs ^a	X												
Consent	X												
Demographic ^b	X												
Operative Data ^f							X						
Length of Stay							X						
Adverse Events ^k	X	X	X	X	X	X	X	X	X	X	X	X	X
Pregnancy Test ^d	X												
SCI (Cervical) ^e	X												
Inclusion/Exclusion	X												
Concomitant Review	X	X	X	X	X	X	X	X					
Procedures	X												
MRI	X		X										
CT	X												
Labs ^c	X	X	X	X	X		X						
ECG(12-lead)	X	X	X	X									
Drug													
Drug Administration ^{i,j}	X	X	X	X									
Serum Biomarkers ^h	X	X		X		X							
Pharmacokinetic ^g	X	X	X	X									
Outcome Measures													
AIS	X	X	X	X	X	X	X	X	X	X	X	X	X
SCIM vIII										X	X	X	

- a. Temperature, blood pressure, pulse, O₂, respiration, BMI, height and weight (can be estimated if patient cannot be measured). Vitals are to be collected at screening (prior to enrolment).
- b. Demographics: age, race, and gender.
- c. Labs: hematology (complete blood count); chemistry (sodium, potassium, chloride, creatinine, electrolytes, bicarbonate, bun); liver function (AST, ALT, bilirubin total, bilirubin direct, and alkaline phosphatase); blood glucose (Blood glucose (BG) monitoring will be hourly (± 30 minutes) for Hours 1-24, every 2 hours (± 30 minutes) for Hours 25-48 and every 4 hours (± 60 minutes) for Hours 49-88. If BG < 70 mg/dL, BG monitoring is required every 15 (± 10 minutes) minutes until BG ≥ 80 for 3 consecutive readings without exogenous bolus glucose supplementation, then hourly (± 30 minutes) for the next 12 hours and every 2 hours (± 30 minutes) thereafter)
- d. Pregnancy test (only complete if woman is of childbearing potential).
- e. SCI (cervical): time, cause, and level of injury.
- f. Optional: only required if patient has surgery.
- g. Blood sampling for PK prior to dosing, at 4-6 hr. (prior to the second dose of glyburide (glyburide), 24±6 hours, 48±6 hours and 60-72 hours. PK samples to be drawn as close as possible to ECGs.
- h. Serum biomarkers: enrollment/baseline, 24 hours, Day 3, and Day 7.
- i. Cannot continue until enrollment liver function test are available and indicate ALT ≤ 3 X upper limit of normal and Bilirubin ≤ 2 X upper limit of normal

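### After glyburide is stopped for low glucose, 5.7 and 6.4 set a shorter glucose watch than 5.8 and the study calendar, and no text says which rule governs

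*Combined protocol and SAP*

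**What the plan says.** Four places state how often to check glucose after a low. All begin alike: every 15 minutes until three consecutive readings of at least 80 mg/dL without bolus glucose (called recovery below). They then part.

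- **Section 5.8**, triggered by any BG below 70: "then hourly (± 30 minutes) for the next 12 hours and every 2 hours (± 30 minutes) thereafter". Its assessments run through day 7 and apply "during and after study drug regimen".
- **Section 5.11, footnote c**: the same rule, hourly "for the next 12 hours and every 2 hours" after that.
- **Section 5.7, Glyburide Discontinuation**, triggered "When glyburide is stopped as a result of low BG": hourly "30 minutes) for the next 6 hours", with no later step.
- **Section 6.4, Blood Glucose**: the same 6-hour ending as 5.7.

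For patients without a low, the base schedule in 5.8 is hourly for Hours 1-24, 2-hourly for Hours 25-48 and 4-hourly for Hours 49-88.

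**The concern.** A patient is stopped for glucose only after one confirmed BG below 55, or three confirmed BG below 70 within 12 hours, despite earlier dose reduction. That patient has already met the 5.8 trigger, so both rules apply, and they ask for different follow-up. A site that opens 5.7 or 6.4 at the moment of stopping would find the shorter rule, for the patients most prone to another low.

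Two things are at stake. One is protection: the step-up after a low keeps a susceptible patient off the 4-hourly schedule. The other is even detection. BG below 55 is a named safety outcome under the primary safety objective. Table 1 in section 3.1 makes a confirmed 55-69 an AE and a confirmed value below 55 an SAE. Sites following different sections would look for repeat lows at different rates.

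**Working it through.** **Step 1: do the triggers overlap?** The stop criteria are BG < 55 once, or BG < 70 three times in 12 hours. Either implies at least one BG < 70, which is the 5.8 trigger, so the overlap is complete. Section 5.8 also covers time after the drug, so it cannot be confined to patients still being dosed. No sentence in 5.7, 5.8, 6.4 or footnote c refers to another of the four places or sets precedence.

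**Step 2: count the checks in the 24 hours after recovery.** Assumptions: nominal times, hours counted from the start of study drug, and a site using 5.7/6.4 goes back to the base schedule after its 6 hours.

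Under 5.8: 12 hourly + 12/2 two-hourly = 18.

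Under 5.7/6.4: 6 hourly + the base-schedule times in the remaining 18 hours. Base times are 1, 2, ..., 24; 26, 28, ..., 48; 52, 56, ..., 88.

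| Recovery at Hour | Base times in the remaining 18 h | Total, 5.7/6.4 | Shortfall from 18 |
|---|---|---|---|
| 12 | 19-24 hourly (6), 26-36 two-hourly (6) | 6 + 12 = 18 | 0 |
| 24 | 32, 34, ..., 48 (9) | 6 + 9 = 15 | 3 |
| 36 | 44, 46, 48, 52, 56, 60 (6) | 6 + 6 = 12 | 6 |
| 48 | 56, 60, 64, 68, 72 (5) | 6 + 5 = 11 | 7 |
| 60 | 68, 72, 76, 80, 84 (5) | 6 + 5 = 11 | 7 |
| 66 | 76, 80, 84, 88 (4) | 6 + 4 = 10 | 8 |
| 72 | 80, 84, 88 (3) | 6 + 3 = 9 | 9 |

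For recovery at Hour 48, for example, the 5.7/6.4 patient is on 4-hourly checks after Hour 54. The 5.8 patient is checked hourly until Hour 60 and 2-hourly after that.

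**Step 3: is drug still present when the 6 hours end?** Section 2.2 describes "low but detectable levels at twenty-four hours" after single doses, and "the terminal half-life being about 10 hours". Taking that half-life alone, with no further dosing, the fraction of the starting level that remains is 0.5^(t/10):

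- 6 hours: 0.5^0.6 = 0.66
- 12 hours: 0.5^1.2 = 0.44

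This is context only. The half-life comes from healthy subjects, the decline is described as biphasic, and a ratio says nothing about the absolute level in a patient whose dose was already reduced.

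**Step 4: how many patients?** The documents give no stop rate at this oral dose. If it were 1% to 5% (assumed), the chance of at least one such patient in 10 would be 1 - 0.99^10 = 0.10 to 1 - 0.95^10 = 0.40.

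**The case against.** The strongest reply is that the rules do not exclude each other. Neither 5.7 nor 6.4 says that it replaces 5.8, and a site that checks hourly for 12 hours has also checked hourly for 6. This stands: a site can comply with all four places by following 5.8. What remains is that nothing tells it to. A shorter watch could also be deliberate because dosing has ended, but the protocol does not say so.

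Other protections stand too. The 6 hours begin only after three readings of at least 80 without bolus glucose, dextrose is given to keep BG above 80, any newly detected BG below 70 restarts the 5.8 step-up, and patients are in intensive care.

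Three stronger readings are tempting, and the documents do not support them.

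- A reader might infer that a stopped patient has only 6 checks after recovery and then none. The base schedule runs to Hour 88, and nothing ends it when glyburide stops.
- A reader might infer that a stop is likely among the 10. In the intravenous phase 1 study, 2 of 26 subjects on drug "were discontinued from the study due to persistent hypoglycemia", and 1 - (24/26)^10 = 0.55. Those two were at 6 and 10 mg/day, against 2.5 to 3.125 mg/day here. Section 2.2 also reports 93 stroke patients at 3 mg/day with no new safety concerns, and a stop here needs earlier dose reduction (two under 5.7, at least one under 6.4).
- A reader might infer that most of the drug is always still on board at 6 hours. That rests on the 10-hour half-life. At an assumed 4-hour half-life, modelling uninterrupted dosing gives as little as 44% of the amount at the stop.

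**Conclusion.** The inconsistency is real and stands in the current text of all four places. For a patient stopped for low glucose, following 5.7/6.4 and then the base schedule means 0 to 9 fewer checks in the 24 hours after recovery than following 5.8. The gap is nil by about Hour 12 and widest for late recovery. This rests on nominal check times and on a return to the base schedule.

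Few of the 10 patients, possibly none, would be affected. Event counts would change only if a stopped patient had a new low that the sparser checks missed, and the documents give no rate for that. No estimand, test, sample size or error rate is involved. It is a minor operational safety correction, worth making because it is cheap and concerns the patients most prone to another low.

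**What to change.** In 5.7 (Glyburide Discontinuation) and 6.4 (Blood Glucose), replace the 6-hour ending with the 5.8 schedule: hourly for 12 hours, then every 2 hours. Put the same end time in 5.7, 5.8, 6.4 and footnote c, for example Hour 88 or 24 hours after the last dose, whichever is later. State that it closes the 2-hourly step and does not cut short the 12 hourly checks. The end time has to go in all four places: a limit in 5.7 and 6.4 alone would leave 5.8 and footnote c open-ended, and a patient with a single reading of 69 would again have the longer watch on paper.

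Cost: a wording change, plus 0 to about 9 extra glucose checks in 24 hours per patient stopped for low glucose. The 9 is counted without an end time. With an end at Hour 88, recovery at Hour 72 would give 12 hourly checks plus Hours 86 and 88, or 14, which is 5 more than 9. Patients with no BG below 70 have no extra checks.
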